 - Staff will then ask whether the patient (if eligible) accepts aPS, and have the patient
 provide written informed consent for the aPS procedures, which include the
 collection of detailed information on the aPS participant's recent sexual partners.
 - Prior to initiating aPS interviews, research staff will explain that all information collected through the aPS process will be kept confidential, and reminded that staff will not reveal index cases' identities when contacting their partners.
 - Index patients who accept aPS will be interviewed using structured interview forms
 that will be used to obtain partner contacts and track partner outcomes.

- Research staff will use a timeline-follow back instrument to elucidate the number of
 unique sex partners that participants have had in the past 1 year for prevalent
 infection and the past 3 months for AHI. If any participant reports injection drug
 use, information about needle-sharing partners will also be elicited.
- For each identified sex partner, staff will collect information including demographic characteristics, contact information, case's relationship to the partner, case's sexual behavior with the partner, and case's knowledge of the partner's HIV status. All data will be collected using structured interview forms and recorded as numerical or categorical outcomes.
- Index cases will be assigned unique identification (ID) numbers and their partners
 will be assigned corresponding numbers that include a random prefix (to protect
 index case confidentiality) and an additional sequential number for each partner,
 allowing partners to be linked to index cases in our dataset.
- aPS intervention participants who are assessed as having a moderate risk for IPV, as
 described in section 13.3.3 under "Rating System for IPV" will undergo special
 monitoring after the aPS consent visit, as described in that section.

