Accounting for correlation within sites (i.e., facilities participating in the randomized trial), precision for the estimated rate of AHI detection is ±0.54%, assuming a prevalence of 1% and k=0.25; if AHI prevalence is 2%, precision will be ±0.81%. For the evaluation of impact and cost-effectiveness, precision is more important than power, since estimates will be used as ranges for modelling. Assuming 150 partners tested as a result of the aPS intervention, we can estimate their HIV prevalence with reasonable precision (binomial confidence limits [CL], 39.8%–56.3%, for 48.0% prevalence); in addition, we will have 80% power to detect a relative risk (RR) of 1.58 or higher for HIV infection in the partners of AHI patients (n=30), compared to partners of prevalent HIV patients (n=120). Assuming 75 new HIV diagnoses from the HIV-1 RNA testing intervention to detect acute and prevalent HIV infection, we can estimate the proportion attaining virologic suppression with reasonable precision (binomial CL, 69.2%–88.3% if 80.0% achieve suppression by month 12); we will have 80% power to detect an RR of 2.84 or higher for failure to suppress among AHI patients (n=15) compared to prevalent HIV patients (n=60).

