15.3. Partner Testing

We will compare the following week 6 outcomes between the observation and intervention periods: (1) number of partners reported; (2) number of partners successfully contacted; (3) number of partners tested; (4) number of partners newly diagnosed with prevalent HIV

infection; (5) number of partners newly diagnosed with AHI (0 in the observation period); (6) number of HIV-infected partners newly engaged in care; (7) number of HIV-uninfected partners initiating PrEP. For PrEP cohort participants (intervention period only) we will also assess the proportion initiating PrEP by month 3 following cohort enrollment and the proportion with adherence >80%, measured by self-report or MEMS® cap at months 3 and 6 following PrEP initiation. The median, inter-quartile range, and range will be presented for each outcome in each period.

Outcomes will also be compared across study periods using Poisson GEE models with a small-sample variance correction [63]. Potential predictors, adjustment for confounding by calendar time, and interaction testing will be as described for the HIV-1 RNA testing intervention analysis above. We will also analyze local sexual network characteristics including the composition of individuals' personal sexual networks by attributes, relational type, relational timing, and relational duration. Characteristics will be compared for partners of index cases with AHI vs. prevalent HIV and for networks that include or do not include one or more AHI cases, using Pearson Chi square or Fisher exact tests for binary outcomes and non-parametric tests for continuous outcomes. We will also conduct a subset of these comparisons to the sexual networks of HIV-negative respondents provided through their CASI/CAPI data. Point estimates and standard errors for each behavioral parameter will be used to parametrize the modelling efforts described below. As above, in analyses in which multiple null hypotheses are tested, p values will be adjusted using the Holm–Bonferroni method.

15.4. Impact and Cost-Effectiveness

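### Partners are listed over 1 year for prevalent index cases but 3 months for acute ones, and the planned acute-versus-prevalent partner comparisons set no common window

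*Combined protocol and SAP*

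**What the plan says.** Section 11.4.2 describes a timeline follow-back interview that counts the unique sex partners "participants have had in the past 1 year for prevalent" "infection and the past 3 months for AHI" (acute HIV infection). The details listed for each partner cover demographics, contact information, relationship, sexual behavior and knowledge of HIV status. A date of last sex is not named.

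Section 15.3 then plans that "Characteristics will be compared for partners of index cases with AHI vs. prevalent HIV", and likewise for networks with and without an AHI case. The network attributes it lists include relational type, timing and duration. It also passes the behavioral estimates and their standard errors to the transmission model.

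Section 14 states that "we will have 80% power to detect a relative risk (RR) of 1.58 or higher" for HIV infection, with 30 partners of AHI patients against 120 partners of prevalent patients. The prevalence behind the adjoining precision statement appears as "39.8%–56.3%, for 48.0% prevalence".

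None of these sections mentions the unequal look-back, a restriction to a common period, or an adjustment for it.

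**The concern.** The look-back differs fourfold, and it is set by the variable that defines the comparison. A partnership that ended between 3 and 12 months before diagnosis can be on a prevalent case's list and, by construction, cannot be on an AHI case's list. Two groups with identical sexual behavior would therefore show different mixes of ongoing and ended partnerships. If infection is more or less common in older partners than in recent ones, they would also show different partner HIV prevalence.

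At stake is the reading of a planned, powered secondary comparison: whether partners of acutely infected people are more often infected, and whether their networks differ. As written, the plan cannot separate such a difference from the effect of the window. Some of these estimates also feed the model. The primary endpoints are not affected.

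**Working it through.** **1. The plan's own figure.** Inputs from section 14: 30 and 120 partners, partner prevalence 48%, relative risk (RR) 1.58, 80% power. Assumptions: 48% applies to partners of prevalent cases, and the test is two-sided at 0.05 (section 14 gives 0.05 for the primary analysis).

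- p1 = 0.48; p2 = 0.48 × 1.58 = 0.7584; difference 0.2784
- pooled p = (120 × 0.48 + 30 × 0.7584)/150 = 0.5357
- SE under the null = √[0.5357 × 0.4643 × (1/120 + 1/30)] = 0.1018
- SE under the alternative = √[0.48 × 0.52/120 + 0.7584 × 0.2416/30] = 0.0905
- power = Φ[(0.2784 − 1.96 × 0.1018)/0.0905] = Φ(0.87) = 80.8%

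The smallest RR with 80% power is 1.575, so the stated 1.58 reproduces.

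**2. What that figure presumes.** Section 14 expects 15 AHI and 60 prevalent index cases. Then 30/15 = 2 and 120/60 = 2: the same number of tested partners per index case in both groups, although one list covers 3 months and the other 12.

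**3. Apparent RR with no true difference.** Let r be the share of 12-month partners who fall within the last 3 months. AHI lists hold recent partners only; prevalent lists hold a mixture.

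Apparent RR = p_recent / [r × p_recent + (1 − r) × p_older]

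The documents give neither r nor p_older, so both are assumed. With p_recent = 0.48:

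| p_older | r = 0.5 | r = 0.8 |
|---|---|---|
| 0.30 | 0.48/0.390 = 1.23 | 0.48/0.444 = 1.08 |
| 0.40 | 0.48/0.440 = 1.09 | 0.48/0.464 = 1.03 |
| 0.60 | 0.48/0.540 = 0.89 | 0.48/0.504 = 0.95 |

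The distortion can go either way, and it vanishes at r = 1 or when older and recent partners have the same prevalence.

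**4. Power at RR 1.58 when partner numbers follow the window** (formula of step 1).

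| Partners, prevalent vs AHI | r = 0.8 | r = 0.5 |
|---|---|---|
| Windows as planned, 120 vs 30r | 120 vs 24: 73% | 120 vs 15: 53% |
| Common 3 months, 120r vs 30r | 96 vs 24: 71% | 60 vs 15: 49% |
| Common 3 months, if 30 is already a 3-month count, 120r vs 30 | 96 vs 30: 79% | 60 vs 30: 73% |

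If the shorter window yields fewer AHI partners, most of the loss is already present under the plan as written. The common window adds about 2 percentage points (73% to 71%) at r = 0.8 and 4 to 5 points (53% to 49%) at r = 0.5.

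**The case against.** **The distortion is small beside the detectable effect.** Apparent RRs of 0.89 to 1.23 are well short of 1.58, and they rest on assumed inputs. This stands as a statement of size: the window alone is unlikely to produce a striking result on HIV infection. It does not remove the bias from the estimate, and it does not cover relational timing and duration, where the 3-month list excludes partnerships that ended earlier.

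**Uniform data already exist.** The CASI/CAPI survey asks all participants the same detailed questions about their three most recent partners (section 11.2.1). This is a partial remedy for network description. Section 15.3 names the survey only for comparison with HIV-negative respondents, and the survey does not determine which partners are traced and tested.

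**The model needs yields as delivered.** Section 15.4 models partner services for prevalent and acute cases as separate scenarios. This is correct, and it is a reason to keep the 12-month results for prevalent cases available, not to leave the direct comparison on unequal windows.

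**Two stronger readings are tempting.** A reader might infer that the window also lowers the intervention period's partner counts, since AHI cases occur only there. The documents do not support this. For the comparison in section 15.3 ("We will compare the following week 6 outcomes between the observation and intervention periods: (1) number of partners reported"), partner outcomes at week 6 are self-reported by the index patient in both periods, with no look-back stated (sections 11.2.2, 11.2.4 and 11.4.1). In the observation period, assisted partner services come only after that self-report. Where the window limits which partners are pursued in the intervention period, that is the intervention as delivered.

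A reader might also infer that AHI cases will list only a quarter as many partners. Section 15.3 does not plan to compare counts between AHI and prevalent cases. A recently infected person will also nearly always have a partner within 3 months: with 1.67 partners per index case, as in the earlier Kenyan trial (section 6.4.4, look-back not stated), one recent partner already gives 1/1.67 = 0.60.

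**Conclusion.** The point holds for the AHI-versus-prevalent comparisons of partner and network characteristics and of partner HIV infection. Followed as written, the plan mixes the look-back with the contrast of interest. The size cannot be fixed from the documents. Under the illustration (r = 0.5, 48% infected among recent partners, 30% to 60% among older ones) the apparent RR runs from 1.23 to 0.89 with no true difference, and it moves closer to 1 as more partnerships are ongoing.

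The stated 80% power is arithmetically right, but it presumes 2 tested partners per index case in both groups. The point does not extend to the observation-versus-intervention counts at week 6. It is worth correcting because the change is cheap, but it concerns a secondary comparison that expects only about 15 AHI index cases.

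**What to change.** Keep elicitation exactly as planned, and change the analysis in section 15.3:

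- For every AHI-versus-prevalent comparison of partners or networks, make the main analysis one of partners within the 3 months before the index case's diagnosis, in both groups.
- Report the 12-month results for prevalent cases separately, so that they remain available for description and for the model.
- Confirm that the follow-back form records a date of last sex for each partner, and add the field if it does not. A timeline follow-back should place partners in time, and section 15.3 already analyses timing and duration, but section 11.4.2 does not list the date.
- In section 14, state the assumed number of tested partners per index case under each window, and present the comparison as an estimate with a confidence interval.
- Leave the week 6 comparison between periods unrestricted. Cutting it to 3 months would discard partners of prevalent cases whose contact, testing and diagnosis are themselves endpoints.

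The cost is possibly one date field, one derived variable and a short paragraph. The common window also leaves fewer partners of prevalent cases: power at RR 1.58 is about 71% if 80% of partners fall within 3 months in both groups, and about 49% if half do.

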11.4.3. Partners of Index Cases Who Consent to APS

- The schedule of procedures for partner testing is detailed in Appendix 21.3.
- When notifying partners, research staff will counsel the partner about HIV and encourage them to test at the nearest KEMRI Research Clinic.
- Partners who are successfully contacted in person will be given a study card with a
 unique ID number linked to the index case's unique ID number to present at the
 nearest KEMRI Research Clinic.
- If contact is established by telephone and the partner agrees to come to the VCT site
 at the nearest KEMRI Research Clinic for HIV-testing, we will send an SMS with an
 ID number linked to the index case's unique ID number, to be used when the partner
 presents for HIV testing.
- Partners who agree to testing in this study will undergo informed consent using an
 informed consent document (ICD) developed for this purpose (Consent 4). If a
 partner refuses to participate in the research study, he or she will be offered VCT in a
 non-research context (i.e., without data collection).
- After consent, the same CASI/CAPI used in the stepped wedge trial (described in section 11.2) will be administered, in order to capture demographic and sexual risk behavior data from participating partners.
- After the CASI/CAPI, the partner will then undergo HIV testing, using standard rapid HIV tests (i.e., standard aPS) for partners of observation period index patients and using the HIV-1 RNA testing intervention (i.e., enhanced aPS) to detect acute and prevalent HIV infection for partners of intervention period index patients.
- If a partner refuses to come to the clinic but consents to enrolment and HIV testing at home, field staff will conduct rapid HIV testing in the home and note the result. For partners of intervention period index patients, blood collected at the partner's home will be transported to the nearest KEMRI Research Clinic laboratory for the XPert®

- HIV Qual test. Field staff will provide these results to intervention period partners within 48 hours and offer further research options (i.e., ART or PrEP cohort enrolment, enhanced aPS if HIV-infected) or referral to HIV prevention services or care as indicated.
- Partners of observation period index patients who are found to be seropositive will
 be offered referral to the local HIV care facility of their preference and will not be
 eligible for the ART cohort at the KEMRI Research Clinics. Partners who test
 seronegative in the observation period will also be referred to local facilities for
 follow-up counseling, and will not be eligible for the PrEP cohort at the KEMRI
 Research Clinics.
- Partners of index patients newly diagnosed with acute or prevalent HIV in the intervention period will be managed as follows:
 - Any partner of an intervention period index patient who is newly diagnosed with acute or prevalent HIV infection will be invited to the nearest KEMRI Research Clinic for enrolment into the ART cohort or offered referral for HIV care, if ART cohort enrolment is declined.
 - All partners of intervention period index patients who are newly diagnosed with acute or prevalent HIV will also be offered enhanced aPS, and their partners will also be offered enhanced aPS, enabling us to thoroughly investigate local sexual networks in which recent transmission occurred.
 - Partners who are uninfected but in an ongoing partnership with any individual newly diagnosed with acute or prevalent HIV infection in the intervention period will be offered enrolment in the PrEP cohort described below.
- All partners who are newly diagnosed with HIV in either study period will be
 assessed at a 6-week follow-up visit to determine linkage to care, ART uptake and
 disclosure to partners.
- At baseline and at the 6-week visit, research staff will counsel newly diagnosed individuals to disclose their HIV status to sexual partners and potential treatment supporters, and provide referral to counseling if needed for that purpose.

11.5. PrEP Cohort for Uninfected Partners in Discordant Partnerships

- Uninfected partners in discordant partnerships will be invited to enroll in the KEMRI Research Clinic PrEP cohort using Consent 6, with prospective follow-up as outlined below. These individuals and their partners will be encouraged to mutually disclose HIV status, in order to avoid potential unintentional disclosures from participating in research at the same research clinic.
- PrEP will be offered as a bridge to virologic suppression by ART in the index patient
 [34]. PrEP will be continued for at least 6 months, or until the HIV-positive partner
 has achieved virologic suppression.
- PrEP medications will be provided at no cost by Gilead, which has agreed to provide PrEP medication for up to 75 participants in this study. Standard tenofovir/emtricitibine dosing will be used, and WHO and Kenyan guidance on PrEP delivery and safety monitoring will be followed.

Version 1.1 17 July 2018 Page **40** of **137**

- We will use MEMS® electronic caps to monitor PrEP adherence in a subset of
 patients who agree to use these devices. We have approximately 50 MEMS® devices
 available from a prior study to use for this purpose. At each refill for participants
 with MEMS® cap pill containers, the electronic data on pill bottle openings since the
 last refill will be uploaded to a database.
- All women who enroll in the PrEP cohort will undergo a family planning assessment
 and offered contraception with injectable depot medroxyprogesterone acetate or oral
 contraceptive pills, both of which are available in the KEMRI Research Clinics. In
 addition, the use of a barrier methods such as condoms will be recommended.
- Patients who enroll in the PrEP cohort will be followed for 12 months, with collection of data as follows for each visit:
 - Baseline visit
 - Confirmation of PrEP cohort eligibility and informed consent
 - Confirmation of contact details
 - Sociodemographic questionnaire
 - Risk assessment questionnaire
 - HIV counseling and testing
 - IPV assessment
 - Risk reduction counseling
 - Mental health assessment
 - Medical history, including family planning assessment
 - Physical examination with collection of vaginal and/or rectal swabs as indicated for STI testing
 - Hepatitis B vaccine (if male-male sex or sex work reported)
 - PrEP counseling and education
 - Counseling and education for contraception (if female)
 - Urine collection for tests per PrEP Cohort Schedule (Appendix 21.5)
 - Blood collection for tests per PrEP Cohort Schedule (Appendix 21.5)
 - o Week 2
 - Confirmation of contact details
 - Risk reduction counseling
 - Qualitative interview (if consents to this procedure)
 - PrEP counseling and initiation
 - MEMS® issuance if willing to use and MEMS® cap available
 - Urine pregnancy testing if applicable

- o Months 1, 2, 4, 5, 7, 8, 10, 11
 - Confirmation of contact details
 - HIV counseling and testing (month 1 only)
 - Risk reduction counseling
 - PrEP counseling, adherence assessment, MEMS® data upload (if applicable), and refills
 - Hepatitis B vaccine dose 2 if indicated (month 1)
 - Urine pregnancy testing if applicable
 - Blood collection for creatinine check (month 1 only)
- o Months 3, 6, 9, and 12
 - Confirmation of contact details
 - Risk assessment questionnaire
 - HIV counseling and testing
 - IPV assessment
 - Risk reduction counseling
 - Medical history
 - Physical examination with collection of vaginal and/or rectal swabs as indicated for STI testing
 - PrEP counseling, adherence assessment, MEMS® data upload (if applicable), and refills
 - Counseling and education for contraception (if female)
 - Qualitative interview (if consents to this procedure)
 - Hepatitis B vaccine dose 3 if indicated (month 6)
 - Urine pregnancy testing if applicable
 - Urine collection from men for STI testing
 - Blood collection for creatinine check (months 3, 6, and 12) and syphilis testing (month 12)
- Month 6 and thereafter
 - Review of need for continued PrEP (i.e., partner ART status and plasma viral load results)
- Additional at Month 12
 - Repeat mental health assessment
 - Urine collection for urinalysis

Version 1.1 17 July 2018 Page **42** of **137**

- Interim visits may occur at any time during PrEP cohort follow-up. All interim
 contacts and visits will be documented in participants' study records and on
 applicable CRFs.
- If a study participant presents to a scheduled or interim visit with symptoms suggestive of acute HIV-1 infection syndrome, an *Xpert*® *HIV Qual* test will be performed and study medication will be held if the patient is newly HIV infected. Any PrEP cohort participant who seroconverts will be offered enrolment in the ART cohort, with 12 months of follow-up, or referred to the HIV care clinic of their choice.
- Mental health assessment at baseline will be conducted by CASI/CAPI, with results
 followed up by our counselors to ensure referral for mental health problems such as
 depression and problem drinking. Our counsellors and clinicians have been trained
 in motivational interviewing and working with peer navigators [59], and will
 encourage patients to take advantage of these services in support of their PrEP
 uptake and adherence.
- If an uninfected partner in a serodiscordant relationship does not accept enrolment into the PrEP cohort, he or she will be counseled on how to reduce HIV transmission risk and referred to another clinic for ongoing follow-up and regular HIV testing in the event that risk persists. PrEP is not currently offered outside of research settings in Kenya, but is expected to become available through government-funded research centers, including to seronegative individuals in serodiscordant partnerships, in the coming months to years. Several PrEP demonstration projects targeting various risk groups (e.g., sex workers, adolescent girls, MSM) are currently at various stages of planning and implementation in Kenya, including in the catchment area for this study.

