6.2. Rationale

Detection and management of AHI has been called a "clinical and public health emergency" [18] and a "common occurrence overlooked" [31]. Because the cost of HIV-1 RNA testing is considerable, there is growing consensus that detection of AHI in resource-limited countries should be guided by algorithms that identify at-risk individuals [32]. While AHI cases have been identified by several research programs in sSA, an evidence-based programmatic approach to targeting testing for young, seronegative adult patients for AHI is lacking. Our novel pilot study (Clinicaltrials.gov, NCT01876199) demonstrating that AHI can be detected in ~1% of young adult patients seeking care forms the basis for this proposal [33]. Our newly developed consensus risk score algorithm will guide targeted AHI evaluation in

patients seeking care for symptoms [26, 33]. We will use a modified stepped wedge design to scale up our HIV-1 RNA testing intervention in a 'proof of concept' study, using the newly available Xpert® HIV Qual commercial assay (which has a lower limit of detection of 278 copies/mL in whole blood) to detect AHI in real time, offer to link patients to care immediately, and offer ART from the day of diagnosis. In addition, we will use aPS to maximize the impact of each new HIV infection diagnosed and linked to care, with standard HIV testing for partners of patients diagnosed in the observation period and the HIV-1 RNA testing intervention for partners of patients diagnosed in the intervention period. As in an ongoing demonstration study in Kenya [34], uninfected partners of all newly diagnosed patients will be provided with PrEP, if accepted, until viral suppression by ART in the index patient. This innovative intervention has the potential to greatly reduce ongoing transmission by making HIV-infected individuals aware of their status and linking them to care without delay, while at the same time identifying HIV-negative persons in discordant couples who would benefit from prevention interventions. If our novel intervention proves cost-effective and promising in terms of reducing HIV-1 transmission, we will use this data to design further research focusing on implementation of the intervention, including barriers and facilitators to its success.

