21.5. Schedule of Procedures, PrEP cohort SCHEDULE OF PROCEDURES, PREP COHORT

Procedures	Visit 1	Visit 2	Visit 3	Visit 4	Visit 5	Visit 6	Visit 7	Visit 8	Visit 9	Visit 10	Visit 11	Visit 12	Visit 13	Visit 14
Visit Month (Study Month = 28 days)	MO	WK 2	M1	M2	М 3	M4	М5	М6	М7	М8	М9	M10	M11	M12
Date of visit														
Eligibility Screening	Х													
Informed Consent (Consent 6)	Х													
Contact Information	Х	Х	Х	Х	Х	Х	Х	Х	X	Х	Х	Х	Х	Х
Sociodemographic Questionnaire	Х													
Risk Assessment Questionnaire	Х				Х			Х			Х			Х
HIV Counseling and Testing ¹	Х		Х		Х			Х			Х			Х
Intimate Partner Violence Assessment	Х				Х			Х			Х			Х
Risk Reduction Counselling	Х	Х	Х	Х	Х	Х	Х	X	X	X	Х	Х	Х	Х
Mental Health Assessment	Х													Х
Medical History	Х				Х			Х			Х			Х
Physical Exam, including collection of vaginal and/or rectal swabs as indicated	х				х			х			х			Х
Hepatitis B vaccination ²	Х		Х					Х						
Qualitative Interview (if consented for this procedure, Consent 7)		х			Х			Х			Х			Х
PrEP Initiation and Refills ³		Х	Х	Х	Х	Х	Х	Х	Х	Х	Х	Х	Х	Х
PrEP Adherence Counselling ³	Х	Х	Х	Х	Х	Х	Х	Х	Х	Х	Х	Х	Х	Х
PrEP Adherence Evaluation ³		Х	Х	Х	Х	Х	Х	Х	Х	Х	Х	Х	Х	Х
Urine Pregnancy Test (women only) ⁴	х	Х	Х	Х	Х	Х	х	х	Х	Х	Х	Х	Х	Х
Urinalysis	Х													Х
Urine collection for STI testing (men only)	Х				Х			Х			Х			Х
Hepatitis B Surface Antigen	Х													

Version 1.1 17 July 2018 Page 88 of 137

Procedures	Visit 1	Visit 2	Visit 3	Visit 4	Visit 5	Visit 6	Visit 7	Visit 8	Visit 9	Visit 10	Visit 11	Visit 12	Visit 13	Visit 14
RPR with TPHA if Positive	X													X
Creatinine	Х		Х		Х			X						X
Sample storage	Х		Х		Х			X			Χ			Χ
Total Blood Volume per Visit (mL)	10	0	4	0	8	0	0	8	0	0	8	0	0	10

- 1. HIV testing will be performed with standard rapid antibody tests at all visits. At baseline, HIV testing will include X-pert® HIV Qual testing to test for AHI.
- 2. HBV vaccination (with doses at baseline, month 1, and month 6) should be provided if at high risk for HBV transmission (i.e., FSW, MSM, or male sex worker), as evaluated by the Risk Assessment Questionnaire administered at the baseline and follow-up visits as above.

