- 3. PrEP will be offered after review of baseline test results (creatinine, HBsAg) to all participants in this seronegative cohort. PrEP will be continued until the seropositive partner has achieved virologic suppression on ART or until the partnership has dissolved, provided the participant does not have a new HIV-infected partner. PrEP counseling will be offered at each visit regardless of uptake. After PrEP initiation, each visit will include adherence counselling, adherence evaluation, and refills until PrEP is discontinued. A MEMS electronic cap will be issued to a subset of participants in order to monitor adherence.
- 4. Pregnancy testing should be provided at every visit. PrEP will be discontinued for any woman who becomes pregnant in the study. Such individuals will be provided HIV risk reduction counseling and referred for antenatal care.

Version 1.1 17 July 2018 Page 89 of 137

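### The rule for ending PrEP differs between section 6.2, section 11.5 and Appendix 21.5, so some partners could be continued under one passage and stopped under another

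*Combined protocol and SAP*

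**What the plan says.** Four places bear on when PrEP ends.

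- **Section 11.5 (PrEP Cohort), duration statement:** "PrEP will be continued for at least 6 months, or until the HIV-positive partner" has reached virologic suppression. The sentence before it describes PrEP as a bridge to that suppression.
- **Appendix 21.5, footnote 3:** "PrEP will be continued until the seropositive partner has achieved virologic suppression on ART or until the partnership has dissolved", with an exception for a participant who has a new HIV-infected partner. No minimum duration is given.
- **Section 6.2 (Rationale):** PrEP is provided, "if accepted, until viral suppression by ART in the index patient". There is neither a minimum nor a rule for the end of the partnership.
- **Section 11.5, visit list, month 6 onwards:** "Review of need for continued PrEP (i.e., partner ART status and plasma viral load results"). The review is scheduled, but the rule it applies is not stated.

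The endpoint concerned is in section 15.3 (and the protocol summary): the proportion with "adherence >80%, measured by self-report or MEMS® cap at months 3 and 6 following PrEP initiation". Neither place states a denominator or how participants no longer on PrEP are counted.

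**The concern.** A minimum duration and an end event are joined by 'or', with nothing to say which prevails. Read one way, six months is a floor that holds even if the index is suppressed earlier. Read the other way, reaching either condition is enough. The appendix and the rationale fit neither reading fully, and they differ from each other on what happens when a partnership ends. Staff working from the schedule of procedures and staff working from section 11.5 could therefore treat the same participant differently.

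Two things are at stake. The first is how long an uninfected partner is protected. The second is the make-up of the group observed at the month-6 adherence measurement: who is on PrEP then depends partly on which passage was followed.

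**Working it through.** **Step 1. The passages side by side.** Section 11.5 is shown under both of its readings.

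| Situation | 11.5, six months as a floor | 11.5, either condition suffices | Appendix 21.5, footnote 3 | 6.2 |
|---|---|---|---|---|
| A. Index suppressed, partner has had under six months of PrEP | continues | may end | ends | ends |
| B. Index unsuppressed at six months, partnership ongoing | continues until suppression, if both conditions are required | may end | continues | continues |
| C. Partnership ends before suppression, no new HIV-infected partner | no such rule | no such rule | ends | no such rule |

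Each row contains at least two different answers.

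**Step 2. When situation A can arise.** The documents state no figure on PrEP duration to reproduce, so this is timeline arithmetic.

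Inputs:
- A study month is 28 days (Appendices 21.4 and 21.5: "Visit Month (Study Month = 28 days").
- "PrEP counseling and initiation" is listed at week 2 of the PrEP cohort (section 11.5).
- Index viral load is scheduled at baseline and at 6 and 12 months after ART initiation (section 12.2).
- L is the number of days from the index's ART start to the partner's enrolment in the PrEP cohort. The documents do not give L. It is negative if the index starts ART after the partner enrols.

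Counting from the index's ART start, and ignoring the time needed to obtain the result:
- Index's first scheduled on-ART viral load: 6 × 28 = day 168.
- PrEP start: day L + 14.
- Partner's cohort month-6 visit, where need is first reviewed: day L + 168. PrEP received by then: (L + 168) − (L + 14) = 154 days, and 154 / 28 = 5.5 study months.
- Six study months of PrEP: day L + 14 + 168 = L + 182.
- Gap from the index's viral load to six months of PrEP: (L + 182) − 168 = L + 14 days.

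| L (assumed) | Index viral load | Cohort month-6 visit | Six months of PrEP | Gap |
|---|---|---|---|---|
| 0 | day 168 | day 168 | day 182 | 14 days |
| 3 | day 168 | day 171 | day 185 | 17 days |
| 14 | day 168 | day 182 | day 196 | 28 days |
| 42 | day 168 | day 210 | day 224 | 56 days |

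During the gap, a suppressed index result ends PrEP under the appendix but not under a six-month floor. The gap grows with late partner enrolment. It closes at L = −14, and if ART starts later than that the viral load comes after six months of PrEP.

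For the month-3 measurement, three study months of PrEP fall on day L + 14 + 84 = L + 98. The index's viral load precedes this only if L + 98 > 168, that is, if L > 70. Month 3 is therefore exposed to the suppression rule only for partners enrolled very late. The dissolution rule can act at any time.

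**Step 3. How many participants.** The ceiling is 75, from the supply limit in section 11.5. The number in situations A to C needs the distribution of L, the proportion of index patients suppressed at month 6, and the rate at which partnerships end. None is given. The only suppression figure is the 80% by month 12 used for precision in section 14, which is not a month-6 value. The number affected cannot be derived.

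**The case against.** The case that this is minor has real content.

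- **The schedule narrows the conflict.** Review of need begins at month 6, and no on-ART index viral load is scheduled before six months of ART. For partners enrolled close to the index's ART start, six months and suppression largely coincide. This stands: situation A mainly concerns late-enrolled partners and those near month 6. It does not help with B or C.
- **Some differences may be elaboration.** Section 6.2 is a one-line rationale. Cohort entry requires an ongoing partnership, so a dissolution rule is a natural extension, and the bridge wording in section 11.5 favours tying PrEP to suppression. This makes some readings more likely than others, but section 11.5 and the appendix are both operating text and still differ.
- **The denominator is a separate gap.** PrEP also stops for pregnancy (Appendix 21.5, footnote 4) and for creatinine events (section 13.3.1), so reconciling duration alone would not define the denominator. This is correct.

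Two stronger readings are tempting, and the documents do not support them.

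1. A reader might infer that every partner of an index patient suppressed at month 6 falls on either side of the rule. That assumes a fixed time relation between the two cohorts. Partners must first be traced, ART may be postponed (sections 11.3 and 17.4), and index patients may decline the ART cohort, leaving no study viral load.
2. A reader might infer that the adherence result could collapse. Suppose 75 starters, 20%, 50% or 80% of index patients suppressed with all their partners stopped, and about 80% adherence in the rest. Those still on PrEP number 60, 37 and 15. Adherence among them is 48/60 = 80%, 30/37 = 81% and 12/15 = 80%; over all 75 it is 48/75 = 64%, 30/75 = 40% and 12/75 = 16%. The lower figures require permitted stops to be counted as non-adherent. Footnote 3 of Appendix 21.5 ends adherence evaluation at discontinuation, which makes that unlikely, and the suppression and adherence inputs are assumptions.

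**Conclusion.** The PrEP end rule is contradictory in current text. Sections 6.2 and 11.5 and Appendix 21.5 can give different decisions when the index is suppressed before the partner has had six months of PrEP, when the index is unsuppressed at six months, and when the partnership ends. The scheduled review does not resolve this, because it names the information to consider and not the rule.

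The consequence is limited. It touches the protection of uninfected partners and the composition of the group at one secondary, descriptive, intervention-period endpoint, mostly at month 6. It concerns at most 75 participants, and the number actually affected is unknown. The primary analysis and its power are unaffected.

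The contradiction rests on the text alone. Only the timing in Step 2 depends on assumptions: 28-day months, PrEP start at week 2, and an assumed enrolment lag.

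**What to change.** 1. The sponsor should reconcile section 6.2, both statements in section 11.5 (duration and month-6 review) and footnote 3 of Appendix 21.5 into one statement. It should say how the minimum, suppression and the end of the partnership relate to each other, and from which date the six months are counted. Which rule to adopt is for the sponsor and is not judged here.
2. In section 15.3, state that the month-3 and month-6 adherence proportions use participants for whom PrEP was still intended at that time under the reconciled statement. Report protocol-permitted stops (suppression, end of partnership, pregnancy, safety holds) separately, by reason.

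The cost is protocol wording, with no added visits, tests or participants. The PrEP cohort consent was not among the pages available for this review and should be checked against the reconciled statement.
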